In the 28-day repeated dose studies in rats and dogs, toxicity findings were consistent with those observed in the range-finding studies. In the rat, DF2755A was administered at dose levels of 60 to 300 mg/kg/day (BID). No mortality occurred during the study and no treatment-related effects were noted in terms of food consumption, ophthalmoscopy or urine parameters. At 300 mg/kg/day, hunched posture and slight salivation were seen together with a lower body weight gain. The same dose level produced slight increases in transaminases. Decreased total protein, total globulin and glucose were seen along with increased lipids. Increased inorganic phosphorus and decreased potassium and calcium were also seen, while decreased urea and creatinine concentrations were observed in females. At histopathology, mixed cell infiltration, oedema, haemorrhage and erosions were noted in the GI tract but showed no dose-dependency and were seen also in control animals. Changes reminiscent of metabolic adaption were seen in the liver and kidneys correlated with increased organ weight and were fully reversible at recovery. Slight atrophy of the thymus, diffuse hypertrophy of the adrenal cortex and reduced secretion in the prostate, coagulating gland and seminal vesicles were also seen at 300 mg/kg/day. Other findings at 300 mg/kg/day included increased incidence of splanchnic haematopoiesis and increased bone marrow cellularity, correlating with decreased RBC count, haemoglobin, haematocrit and mean corpuscular haemoglobin and increased relative reticulocytes; all these changes were reversible at recovery. Slight increases in WBCs correlated with the inflammatory changes seen in the stomach. In the dog, repeated administration of DF2755A at dose levels in the range 40 to 200 mg/kg/day was generally well tolerated and no effects on body weight, food consumption, ophthalmoscopy, ECG examination or clinical pathology parameters were seen at any dose. Macroscopic findings included discolouration of the ileocaecal valve and reddish foci in the colon, rectum and pylorus. Upon microscopic examination, haemorrhage or congestion in the ileocaecal valve and/or colon as well as haemorrhage, erosion, mixed cell infiltration, and congestion of the pylorus were observed. Centrilobular hepatocellular hypertrophy was observed in females at mid and high dose and correlated with increased liver weights, but was not associated with any degenerative or inflammatory changes. In both species, the GI effects are similar to effects seen with other propionic acid derivative and likely a class effect, while the liver and kidney changes are considered to represent an adaptive metabolic phenomenon and of limited toxicological concern. The dose of 120 mg/kg/day was considered to be the NOAEL for repeated 4-week oral administration in the rat, while the NOAEL in the dog was 40 mg/kg/day.

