
Electron microscopy investigation in the liver of rats indicated the presence in the hepatocytes of areas of low electron-density and homogeneous appearance interspersed among the mitochondria and

rough endoplasmatic reticulum. However, no indication of cellular or organelles alterations were observed.

The *in vitro* genetic toxicity test for bacterial mutations (Ames assay) and chromosomal aberrations in human lymphocytes revealed no genotoxic potential for DF2755A. No evidence of clastogenicity or aneugenicity was found in the rat micronucleus test following administration of DF2755A by oral gavage up to the maximum tolerated dose level of 300 mg/kg/day.

A male and female fertility study combined with embryo-fetal development study with DF2755A Monohydrate was done in rats by oral gavage. Ninety-six male and ninety-six main female Wistar Han rats were assigned to four dose groups. The test item was administered once daily by oral gavage at doses of 50, 100 and 150 mg/kg (Groups 2, 3 and 4 respectively). The rats of the control group received the vehicle, water, alone. In addition, five satellite animals (females only) per treatment group and three satellite females in the control group were exposed and used for toxicokinetic blood sampling on Day 17 post-coitum. Males were exposed for 43-46 days, i.e. 2 weeks prior to mating, during mating, and up to termination. Mated females were exposed for 33-46 days, i.e. during 2 weeks prior to mating, during mating, and continuing until Day 17 post-coitum, inclusively. Females without evidence of mating were dosed until one day prior to euthanasia.

No reproduction and developmental toxicity was observed up to a dose level of 150 mg/kg. A slight, treatment related decrease in body weight gain was observed in males treated at 150 mg/kg from Day 4 of treatment onwards, resulting in approximately 5% lower absolute body weights at the end of treatment. As this effect was very small and no concurrent effect on food consumption was noted, this was considered not to be adverse.

No maternal toxicity was observed in females at any dose groups.

In conclusion the NOAEL to be considered for the calculation of the maximum recommended starting dose (MRSD) in humans are:

TOX 4 week (28 day) and corresponding exposure levels

RAT:	NOAEL 120 mg/kg (60 mg/kg b.id.)	C _{max_{ss}}	193 µg/mL	AUC _{ss(0-24)}	2275 h*µg/mL
DOG:	NOAEL 40 mg/kg (20 mg/kg b.id.)	C _{max_{ss}}	18.00 µg/mL	AUC _{ss(0-24)}	81.75 h*µg/mL

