1.4. Description and justification for the dosage regimen

Doses were calculated using the body surface area conversion. The calculated maximum recommended starting dose (MRSD) is 117 mg in rats and 130 mg in dogs. Based on data available for the rat, the proposed MRSD is 50 mg/subject, 23 times lower than the HED at NOAEL. As general rule the human equivalent efficacy dose is higher than the efficacy dose obtained in animals.

A prediction of the human PK parameters and the human equivalent pharmacological dose of DF2755A using allometric scale simulation has been carried out using the information on efficacy in rats.

Pharmacologic HED was calculated using the estimated (scaled) human clearance and the AUC that resulted in pharmacological activity. Pharmacologic HED ranged from 77 to 3202 mg BID (i.e. 144 -6404 mg) depending on the rat efficacious exposure and projected CL used. Considering these results, the dose of 50 mg could be considered the suitable first dose in human due to the fact that it is lower than the projected human pharmacological equivalent dose by a factor >7 or >10 if 7 or 10 mg/kg are considered the efficacy doses in rats, respectively.

These results are in agreement, see above, with the HED calculated from the 4-week oral toxicity study in rat were applying a safety factor of 23-fold the starting dose results to be 50 mg.

To preserve the safety of the subjects after the first cohort (PK parameters permitting) a PK simulation to determine the predicted PK parameters at the higher dose/s will be performed to predict the expected exposure.

The following single doses are planned to be administered in Part A:

Table 8: Doses for administration in Part A

Proposed Doses		SAD		
Human Equivalent dose (HED) considering the more sensitive species (RAT) mg/kg	Dose mg/subj (60kg)	Dose mg/kg	Safety margin	Ratio
19.44	50	0.83	23.33	
	150	2.50	7.78	3
	450	7.50	2.59	3
	700	11.67	1.67	1.55

The maximum dose of 700 mg is in the range of the pharmacological HED and it is in the range of the exposure covered by the toxicological studies.

The first MAD cohort will be initiated only after the authorization, from ANSM of a substantial amendment that will be presented in order to notify the results of SAD part of the study.

The anticipated doses tested in Part B are the following:

Table 9: Doses for administration in Part B

Proposed Doses		MAD (proposed 14 days) b.i.d.			

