3.3.3.2. Dose Escalation

The dose escalation is designed to progress from the first to the highest dose up to the occurrence of relevant events supporting Maximal Tolerated Dose (MTD) determination.

At the end of each dose level, an interim safety report will be issued by the Investigator. A dose escalation teleconference meeting will be held between the Investigator and the Sponsor representatives, and the decision on how to proceed (e.g. next higher dose) will be taken on the basis of a blind safety and pharmacokinetic data review.

The following safety parameters will be reviewed for both part, for all the subjects:

- Any adverse events reported;
- All laboratory parameters outside of ranges;

- Concomitant therapy;
- Physical examination abnormalities;
- Vital signs abnormalities;
- ECG abnormalities.

For dose escalation, Pharmacokinetic data on plasma (quantitative determination of DF2755A bound and unbound; qualitative and preliminary quantitative determination of known metabolites), urine and faeces recovery (qualitative and quantitative determination of parent compound and qualitative and preliminary quantitative investigation of known metabolites) will be considered by using, for each new dose level, the pharmacokinetic results of the previous dose level in order to re-estimate the safety margin based on the animal-human exposure ratio. This re-estimation must be taken into account when deciding whether to proceed to the next dose level.

The exposure does not exceed the AUC of 1000 $\mu\text{g}\cdot\text{h}/\text{mL}$.

Identification of non-acceptable risks or significant proportion of AEs with common pathological pattern can justify the modification of the dose escalation design.

After mutual agreement between the Sponsor and the Investigator and if it is considered useful for the selection of the next dose level, the treatment of a specific subject and/or a cohort may be unblinded before the next dose level of DF 2755A is administered.

At the end of the teleconference meeting, the following decisions can be taken:

- Dose escalation will continue as scheduled;
- An intermediate dose between the current dose and the following dose will be administered to the next cohort;
- A lower intermediate dose, between the current dose and the dose administered in the previous cohort will be administered to the next cohort;
- The current dose will be repeated in the next cohort;
- The study will be stopped.

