3.5.4. Stopping rule for dose escalation

The safety review committee will decide to stop the dose escalation as planned per protocol in case of occurrence of:

- 2 subjects experiencing severe non serious AEs of the same organ class and nature related to the study drug,
- 4 subjects (for SAD) and 8 subjects (for MAD) experiencing study drug related moderate non serious AEs (that are considered directly related to the drug effect unless they resolved despite the continuation of the treatment),
- 2 subjects of the group experience a significant increase (i.e. $> 3 N$) ALAT,
- 2 subjects of the group experience simultaneous increases of total bilirubin ($> 2 N$), ALAT ($> 2 N$) and alkaline phosphatases ($> 1.5 N$),

- 2 subjects has a sustained QTc value > 500 ms (confirmed by a second ECG under strict resting position),
- One subject presents a C_{max} or $AUC_{(0-24h)}$ values respectively above 150 $\mu\text{g}/\text{mL}$ and 1000 $\mu\text{g}/\text{mL} \cdot \text{h}$,
- The mean C_{max} and $AUC_{(0-24h)}$ leads to believe taking into account the dose increase that C_{max} or $AUC_{(0-24h)}$ values of 125 $\mu\text{g}/\text{mL}$ and 600 $\mu\text{g}/\text{mL} \cdot \text{h}$ will be overpass with the following planned higher dose,
- In MAD part the mean at the steady state C_{max} and $AUC_{(t)}$ leads to believe taking into account the dose increase that C_{max} or $AUC_{(0-24h)}$ values of 125 $\mu\text{g}/\text{mL}$ and 800 $\mu\text{g}/\text{mL} \cdot \text{h}$ will be overpass with the following planned higher dose,

In one of the cases listed above, the dose group in progress will be stopped and the blind could be broken. Regarding laboratory and QTc abnormalities described above, if unblinding confirms that at least two subjects presenting these abnormalities were receiving the active drug the dose escalation will be stopped.

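### Every exposure limit that stops escalation lies below the rat NOAEL exposure but several-fold above the dog NOAEL exposure, and the plan does not say which species the limits rest on

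*Protocol*

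**What the plan says.** Protocol 3.5.4 lists the exposure criteria that end escalation. One concerns a single subject: "One subject presents a C_{max} or $AUC_{(0-24h)}$ values respectively above 150" µg/mL and 1000 µg·h/mL. The others concern the mean projected to the next dose, where the observed mean "leads to believe taking into account the dose increase that C_{max} or $AUC_{(0-24h)}$ values of 125" µg/mL and 600 µg·h/mL would be exceeded; the MAD version uses 125 and 800. Section 3.3.3.2 repeats one limit: "The exposure does not exceed the AUC of 1000" µg·h/mL. Neither section says how the limits were derived, which species they refer to, or whether they mean total or unbound drug.

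Section 3.3.3.2 also requires the meeting, for each new dose level, to "re-estimate the safety margin based on the animal-human exposure ratio" and to weigh the result in its decision. It names no species and no minimum ratio.

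Tables 8 and 9 head their margin column with "Human Equivalent dose (HED) considering the more sensitive species (RAT) mg/kg" and print margins only as HED divided by dose, both in mg/kg. Section 1.3 rests the adequacy of the margins on rat and dog toxicology. Section 1.4 says of the 700 mg dose that "it is in the range of the exposure covered by the toxicological studies", without figures. Section 1.2.1.4 sets the NOAEL at 120 mg/kg/day in the rat; for the dog it gives "NOAEL 40 mg/kg (20 mg/kg b.id".), the lowest dose in that study, and lists steady-state exposures for both species.

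**The concern.** The escalation decision is meant to use exposure, but the printed margins use body-surface-scaled dose, and the two scales rank the species differently. On HED the rat gives the smaller margin. On plasma exposure the dog NOAEL sits far below the rat NOAEL. A limit can therefore look conservative against the rat and still be several times the dog value.

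This matters because these are the quantitative exposure stops in a first-in-human study. A meeting that follows the text can compute its exposure ratio against the rat alone, see a comfortable figure beside printed margins of 1.67 (700 mg) or 1.94 (300 mg bid), and stay within every limit in 3.5.4, with human exposure several times the exposure at the dog NOAEL. Above that NOAEL the dog study had further findings; 1.2.1.4 describes gastrointestinal haemorrhage, erosion and congestion.

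**Working it through.** **1. Reproduce the printed margins.** HED 19.44 mg/kg, body weight 60 kg. Table 8, 700 mg: 19.44 / (700/60) = 1.67. Table 9, 600 mg per day: 19.44 / (600/60) = 1.94. Both agree with the protocol. The starting doses in 1.4 (117 mg rat, 130 mg dog) confirm that the rat is the stricter species on this scale.

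**2. Check the NOAEL exposures in 1.2.1.4 against Tables 5 and 6** (Week 4, mean of male and female).

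- Dog, 20 mg/kg bid: the four peaks 18.8, 17.4, 19.2 and 16.7 average 18.03, so the printed Cmax of 18.00 µg/mL reproduces. The printed AUCss(0-24) of 81.75 equals (77.2 + 86.3)/2, which is AUC8-24. The 24 h value (AUClast, with tlast at 24 h) is (118 + 136)/2 = 127.
- Rat, 60 mg/kg bid: the printed Cmax of 193 µg/mL equals the second-dose mean (164 + 222)/2. The printed AUCss(0-24) of 2275 equals (1960 + 2590)/2, again AUC8-24. The 24 h value is (3000 + 3790)/2 = 3395.

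The 0-24 h label in 1.2.1.4 is therefore wrong for both species. The calculations below use 127 and 3395.

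**3. Compare the species on exposure.** Rat/dog: Cmax 193/18.00 = 10.7; AUC 3395/127 = 26.7. On exposure the dog is the more sensitive species.

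**4. Divide each limit by the NOAEL exposures.** The unbound ratio is (limit × 0.0252) / (dog value × 0.073), from the stated binding of 97.48% in human and 92.7% in dog plasma.

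| Limit in 3.5.4 | ÷ dog NOAEL, total | ÷ dog NOAEL, unbound | ÷ rat NOAEL, total |
|---|---|---|---|
| Cmax 125, projected mean | 125/18.00 = 6.9 | 2.4 | 125/193 = 0.65 |
| Cmax 150, one subject | 150/18.00 = 8.3 | 2.9 | 150/193 = 0.78 |
| AUC 600, projected mean | 600/127 = 4.7 | 1.6 | 600/3395 = 0.18 |
| AUC 800, projected mean, MAD | 800/127 = 6.3 | 2.2 | 800/3395 = 0.24 |
| AUC 1000, one subject | 1000/127 = 7.9 | 2.7 | 1000/3395 = 0.29 |

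A reader who uses the AUCs as printed in 1.2.1.4 will get 600/81.75 = 7.3, 800/81.75 = 9.8 and 1000/81.75 = 12.2 for the dog, and 0.26, 0.35 and 0.44 for the rat (against 2275). The direction is the same.

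**5. Compare with the top dog group (100 mg/kg bid, Table 6).** Week 4 means: first-dose Cmax (120 + 130)/2 = 125 and AUC (822 + 878)/2 = 850, so the single-subject limits are 150/125 = 1.2 and 1000/850 = 1.18 times these. Day 1: AUClast was 1080 and 1070, and the higher peak in each sex was 168 and 160, all above the limits.

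**The case against.** Several points on the other side have force.

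- *A reader might infer that the limits contradict 3.3.3.2.* They do not. A fixed ceiling and a margin review at each step can coexist. The gap is that neither names a species.
- *The rat label might look like an error.* It is correct on the HED basis in the column heading. It becomes misleading only when carried over to an exposure-based decision.
- *It is tempting to say that the single-subject limits exceed anything seen in the top dog group.* That is true of the Week 4 means only. Day 1 values in the same group lie above the limits, and the single-dose radiolabel study in dogs (Table 3) reports parent-drug Cmax of 127 and 194 µg/mL. These give some support to the sentence in 1.4 about exposure covered by toxicology. They do not move the NOAEL exposure.
- *The comparator is strict for Part A.* It is a 28-day twice-daily steady-state NOAEL set against single doses. This stands as a limitation, although Table 8 itself uses the 28-day rat NOAEL for the single doses, and Part B doses for 14 days.
- *Protein binding narrows the gap.* It does, to about 1.6 to 2.9. But binding was measured at 3.383 µg/mL in human and 48.5 µg/mL in dog plasma and is described as saturable, so the human free fraction near the limits is unknown. If it rises with concentration, the unbound ratios are underestimates.
- *The toxicology is milder than the findings alone suggest.* Section 1.2.1.4 also reports good overall tolerability in the dog, no clinical pathology changes at any dose, and a probable class explanation for the gut findings. That could justify exceeding the dog NOAEL exposure, but nothing in the protocol links it to the limits.
- *Other safeguards exist:* a PK simulation after cohort 1, Part B doses that may be changed, and regulatory authorisation before MAD. None fixes the species used for the ratio.

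**Conclusion.** The concern holds in this form: all the exposure limits in 3.5.4 lie below the rat NOAEL exposure and above the dog NOAEL exposure, by 6.9 to 8.3 times on Cmax and 4.7 to 7.9 times on AUC over 24 h (total drug), and the protocol gives neither a species nor a rationale. The most sensitive species depends on the scale: rat on body-surface dose, dog on exposure (about 11-fold on Cmax and 27-fold on AUC).

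The figures rest on Week 4 means in Tables 5 and 6, on reading the limits as total concentration, and, for the unbound ratios, on the stated binding percentages.

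A reader might infer that volunteers will be exposed above the dog NOAEL level. The documents do not support that step: no human Cmax or AUC is printed for any planned dose, so whether 700 mg or 300 mg bid would come near the limits is unknown. What is established is that the limits, as written, would not prevent it. Separately, the AUCss(0-24) values in 1.2.1.4 are mislabelled for both species.

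**What to change.** 1. In 1.2.1.4, correct the AUC(0-24) values at the NOAELs from Tables 5 and 6 (24 h means of 3395 for the rat and 127 for the dog), or relabel the printed values as AUC8-24.
2. In 3.3.3.2, require each escalation meeting to compute the animal-human exposure ratio for Cmax and AUC0-24, total and unbound, against both the rat and the dog NOAEL, using the human PK observed so far. Exposure margins cannot be added to Tables 8 and 9 in advance from the existing tables, because these contain no human exposure.
3. In Tables 8 and 9, state that the species label and margins hold on body-surface scaling.
4. Have the sponsor reconcile the limits in 3.5.4 and 3.3.3.2 with the dog NOAEL exposure and with the statements in 1.3 and 1.4, either by stating the species, the exposure basis (total or unbound) and the reason why exceeding the dog value is acceptable, or by revising the limits. No limit or dose is proposed here; that is for the sponsor and the authority.

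Items 1 to 3 cost protocol wording and a few extra ratios per meeting. The price is that the stated margins become less favourable, and escalation may end earlier if the sponsor revises the limits.

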AUC₀₋₂₄	:	Area under the plasma concentration-time curve from time zero to 24 hours post-dosing
AUC₀₋₇₂	:	Area under the plasma concentration-time curve from time zero to 72 hours post-dosing
AUC_τ	:	Area under the plasma concentration-time curve within a 12-hour dosing interval at steady state
CL/F	:	Apparent clearance
CL_R	:	Renal clearance
CL_{ss/F}	:	CL/F at steady state

C_{max}	Maximum plasma concentration
C_{ss,av}	Average plasma concentration at steady state
C_{ss,max}	Maximum plasma concentration at steady state
C_{ss,min}	Measured plasma concentration at the end of the dosing interval
PK	Pharmacokinetic(s)
PTF%	Peak trough fluctuation
t_½	Terminal half-life
t_{max}	Time of maximum plasma concentration
t_{ss,max}	Time to maximum plasma concentration at steady state
V_d :	Apparent volume of distribution
V_{dss} :	Apparent volume of distribution at steady state
λ_z	Terminal phase rate constant

Data Management & Statistics

CI	:	Confidence Interval
DCF	:	Data Clarification Form
DRF	:	Data Resolution Form
eCRF	:	Electronic Case Report Form
GM		Geometric mean
Min		Minimum
Max		Maximum
N		Number
SD	:	Standard Deviation
SEM	:	Standard Error of the Mean

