t_{lag} The time before occurrence of the first quantifiable plasma concentration will also be obtained directly from the concentration-time data; it is the time point immediately prior to the first quantifiable plasma concentration.

λz The terminal plasma elimination rate-constant will be estimated from log-linear regression analysis of the terminal phase of the plasma concentration *vs.* time profile (SAD part and MAD part Day 14 only). For the slope of the terminal elimination phase to be accepted as reliable, the following criteria will be imposed:

- a coefficient $r^2 \geq 0.90$,
- a minimum of 3 data points, including the last measured data point and excluding C_{max} , are available for the regression.

If these 2 criteria could not be met, the slope of the terminal elimination phase will be considered as not calculable and all the parameters derived from this value ($AUC_{0-\infty}$, $t_{1/2}$, ...) will be reported as not calculable (NC).

t_{1/2} $t_{1/2}$ will be calculated according to the following equation: $t_{1/2} = \ln 2 / \lambda z$ (SAD part and MAD part Day 14 only).

AUC_{0-t} The area under the concentration *vs.* time curve over the dosing interval will be calculated using a linear trapezoidal method (*i.e.* from time zero (pre-dose) to 12 h post-dose in MAD part only).

AUC₀₋₂₄ The area under the concentration *vs.* time curve from time zero (pre-dose) to 24 h post-dose will be calculated using a linear trapezoidal method (SAD part only).

AUC_{0-t} The area under the concentration *vs.* time curve from time zero (pre-dose) to the time of last quantifiable concentration will be calculated using a linear trapezoidal method.

AUC_{0-∞} The area under the serum drug concentration *vs.* time curve from time zero to infinity: $[AUC_{0-\infty} = AUC_{0-t} + (C_t/ke)]$, where C_t = the observed concentration of drug for the last sample on the PK profile in which drug was detected, and ke as defined above. The percentage of extrapolation of $AUC_{0-\infty}$ should normally not exceed 20% to consider the value as reliable (SAD part only).

fu Fraction of unbound in plasma

Cl/F The apparent volume of the central compartment cleared of drug per unit time will be estimated using the formula (DF 2577Y only in SAD part only).

$$Cl/F = \text{Dose} / AUC_{0-\infty}$$

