6.2. Specification of pharmacokinetic parameters

Part A:

The following pharmacokinetic parameters will be determined from DF2755Y (the acid form of DF2755A and for metabolites if any):

- C_{max} (ng/mL);
- t_{max} (h);
- λ_Z ;
- $t_{1/2}(h)$;
- AUC_{0-24} (h \times ng/mL);
- AUC_{0-t} (h \times ng/mL);
- $AUC_{0-\infty}$ (h \times ng/mL);
- fu
- V_Z/F (DF2577Y only);
- CL/F (DF2577Y only);
- Ae_{0-24} and AUC_{0-last} ;
- fe_{0-24} and fe_{0-last} ;
- CL_R ;
- Total amount in faeces;
- Parent:metabolite(s) ratio for C_{max} and AUCs..

Part B:

The following pharmacokinetic parameters will be determined from DF2577Y (the acid form of DF2755A and for metabolites if any):

Day 1

- C_{max} (ng/mL);
- t_{max} (h);
- t_{lag} (h);
- λ_Z ;
- $t_{1/2}$ (h);
- AUC_{0-12} (h \times ng/mL);
- Ae_{0-12} and Ae_{0-24} ;
- fu ;
- fe (%);
- CL_R : renal clearance;
- Parent:metabolite(s) ratio for C_{max} and AUCs.

Day 14

- $C_{ss,max}$ (ng/mL);
- $t_{ss,max}$ (h);
- t_{lag} (h); $C_{ss,min}$ (ng/mL): measured plasma concentration at the end of the dosing interval;
- λ_Z : terminal phase rate constant;
- $t_{1/2}$ (h): terminal half-life;
- AUC_{0-t} (h \times ng/mL);
- $C_{ss,av}$ (ng/mL);
- fu ;
- Ae_{0-last} ;
- Total amount in faeces;
- Parent:metabolite(s) ratio;
- Accumulation ratios for C_{max} and AUC_{0-12} .

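### The NOAEL exposures labelled AUCss(0-24) are 8-24 h values, so the animal-human exposure ratio is understated; the 24 h AUC used in Part B escalation should also be defined

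*Protocol*

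**What the plan says.** **Animal exposure.** Section 1.2.1.4 ends with the NOAEL doses and their steady-state exposures. The rat AUCss(0-24) is given as 2275 h·µg/mL (60 mg/kg bid) and the dog value as 81.75 h·µg/mL (20 mg/kg bid). Section 3.3.3.2 says that human PK from each dose level is used to "re-estimate the safety margin based on the animal-human exposure ratio", and that this must be weighed before the next step.

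**Exposure limits.** Section 3.3.3.2 adds "The exposure does not exceed the AUC of 1000" µg·h/mL and gives no time window. Section 3.5.4 stops escalation if "One subject presents a C_{max} or $AUC_{(0-24h)}$ values respectively above 150" µg/mL and 1000 µg·h/mL. For Part B it also has a projection rule: "In MAD part the mean at the steady state C_{max} and $AUC_{(t)}$ leads to believe taking into account the dose increase", with limits at the next dose of 125 µg/mL for Cmax or 800 µg·h/mL for AUC(0-24h).

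**AUC definitions.** The abbreviation list defines the steady-state interval AUC as "Area under the plasma concentration-time curve within a 12-hour dosing interval at steady state". Section 6.1 takes the dosing-interval AUC "from time zero (pre-dose) to 12 h post-dose in MAD part only" and the other AUC "to 24 h post-dose will be calculated using a linear trapezoidal method (SAD part only". The Part B lists in Section 6.2 contain no AUC0-24, and accumulation is on the 12 h value ("Accumulation ratios for C_{max} and AUC_{0-12"). Section 6.1 does ask for renal clearance to 24 h on Day 1 of Part B. The PK methods in the SAP are written for Part A.

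**The concern.** The exposure ratio is a required input to every escalation decision in healthy volunteers, so its animal side should cover the window its label claims. In the toxicology studies the second daily dose was given at 8 h, so an AUC8-24 leaves out the whole first dosing interval of the day.

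Part B has a related gap. With bid dosing, 24 h holds two doses. The Part A projection rule has AUC(0-24h) on both sides. The Part B rule starts from the interval AUC and ends at AUC(0-24h), without saying how one becomes the other. A rule that stops dosing should be executable as written, especially when one group derives the PK and others decide by teleconference.

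The Day 1 renal clearance to 24 h in Part B needs a 24 h AUC across an evening dose that is followed by only two samples, at T16h and T24h.

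**Working it through.** **1. Reproducing the printed NOAEL figures.** Inputs are the Week 4 male and female values at the NOAEL dose, from Section 1.2.1.3, Table 5 (rat, 60 mg/kg bid) and Table 6 (dog, 20 mg/kg bid). Formula: (male + female)/2.

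| Week 4 AUC, h·µg/mL | Rat | Dog |
|---|---|---|
| 0-8 h | (1040 + 1200)/2 = 1120 | (41.0 + 50.1)/2 = 45.55 |
| 8-24 h | (1960 + 2590)/2 = **2275** | (77.2 + 86.3)/2 = **81.75** |
| AUClast (last sample at 24 h) | (3000 + 3790)/2 = **3395** | (118 + 136)/2 = **127** |
| Printed as AUCss(0-24) | 2275 | 81.75 |

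The 8-24 h row matches both printed figures exactly. No Day 1 row, other interval or geometric mean does. As a check, 1120 + 2275 = 3395 and 45.55 + 81.75 = 127.3, which is 127 within rounding.

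**2. Size of the error.** Rat: 3395/2275 = 1.49, so the printed value is 33% too low. Dog: 127/81.75 = 1.55, or 36% too low. As an illustration, take a human AUC(0-24h) of 800 µg·h/mL. The rat ratio is 2275/800 = 2.84 as printed and 3395/800 = 4.24 corrected. The dog ratio moves from 0.10 to 0.16.

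**3. Part B thresholds on the 12 h scale.** Assume two like dosing intervals and dose-linear scaling. The limit of 800 at the next dose corresponds to these current AUC0-12 values:
- 100 to 200 mg bid: 800/2/2 = 200. Without the conversion it would be 800/2 = 400.
- 200 to 300 mg bid: 800/1.5/2 = 267. Without the conversion, 800/1.5 = 533.
- Single-subject limit: 1000/2 = 500, against 1000.

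**4. Is doubling adequate?** Human PK is not given, so I assumed a one-compartment oral model with half-life 3, 5 or 8 h and tmax 0.5, 1 or 2 h (nine scenarios). I applied the linear trapezoid at the planned sampling times. Twice the Day 14 AUC0-12 recovers 0.975-0.996 of the true daily AUC.

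**5. Would the Cmax limit catch a misreading?** If a 12 h AUC were wrongly set against 800 or 1000, the daily AUC could reach 2 × 800 = 1600 (mean) or 2 × 1000 = 2000 (one subject) on the AUC criterion alone. In the same scenarios, mean Cmax passes 125 µg/mL before a daily AUC of 1600 in 4 of 9, at 1136-1576. One subject passes 150 µg/mL before 2000 in 5 of 9, at 1363-1996. At the 8 h half-life the Cmax limit does not trip first in any scenario.

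**6. Day 1 renal clearance in Part B.** Clearance is amount excreted divided by AUC, so its bias is the inverse of the AUC bias. With T12h, T16h and T24h around the evening dose, the trapezoid gives 0.832-0.930 of the true AUC0-24 in the nine scenarios. AUC therefore reads 7-17% low. Clearance reads 1/0.930 = 1.075 to 1/0.832 = 1.20 times the true value, about 8-20% high.

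**The case against.** **On the NOAEL figures.** The error makes animal exposure look smaller, so the human margin looks tighter than it is. The correct 24 h values are printed in Tables 5 and 6. Starting and planned doses came from body-surface-area conversion of mg/kg doses (Section 1.4), not from these AUCs. All of this stands. A reader might infer that the 600, 800 and 1000 limits rest on the wrong figures, but no text derives them from the NOAEL AUCs. What remains is a wrong number that feeds a mandatory step.

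**On Part B.** A reader might infer that the stopping rule lets twice the intended exposure through. The documents do not support that. Section 3.5.4 labels both 800 and 1000 as AUC(0-24h), so setting a 12 h AUC against them contradicts the printed rule. Doubling is the evident intent: the average steady-state concentration is already a Day 14 parameter, and 24 times it is the daily AUC. Cmax is an alternative trigger and would catch part of any misreading. The 1000 cap in Section 3.3.3.2 has the same value as a limit that Section 3.5.4 does label as 24 h.

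Nor can one say that Part B has no route to a 24 h AUC. Days 1 and 14 are sampled to T24h, and Section 6.1 requires a 24 h AUC for Day 1 clearance. The Day 14 list prints AUC0-t, probably a lost tau. What stands is that the conversion is unwritten, and that direct integration to 24 h would be coarse after the evening dose.

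**On renal clearance.** No stopping rule uses it, and the bias depends on assumed human kinetics. That is fair; it is a secondary point.

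**Conclusion.** The labelled NOAEL exposures are wrong as written. The Week 4 24 h means are rat 3395 and dog 127 h·µg/mL, 1.49 and 1.55 times the printed values. This follows from the protocol's own tables without assumptions. The effect on escalation assumes that the team takes the animal side of the ratio from the Section 1.2.1.4 summary and sets it against a human 24 h AUC. The margin is then understated, which is the conservative direction.

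The Part B AUC point is a clarification of a rule already labelled 0-24 h. No miscalculation is shown. The Day 1 clearance point is valid but minor. Its 8-20% upward bias holds for an assumed half-life of 3-8 h and tmax of 0.5-2 h.

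**What to change.** - **Section 1.2.1.4:** change AUCss(0-24) to rat 3395 and dog 127 h·µg/mL, and use these in every exposure ratio.
- **Section 3.5.4:** state that in Part B the AUC(0-24h) compared with 800 and 1000 is 2 × the Day 14 AUC0-12, for each subject and for the mean.
- **Section 3.3.3.2:** give the cap of 1000 the same 24 h window.
- **Section 6.1, Day 1 of Part B:** report renal clearance over 0-12 h only.

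Cost: text only, in the substantial amendment already required before Part B. No extra subjects, samples or assays are needed. The downside is the loss of the 24 h clearance estimate on Day 1. If that estimate is wanted, added T13h and T14h samples would bring the AUC0-24 to 0.982-1.039 of true under the same assumptions. They would cost 2 × 6 = 12 mL per subject (435.9 to 447.9 mL) and 2 × 36 = 72 assays.
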